9.4.2.3 HANDLING OF DROPOUTS AND MISSING DATA

Every effort should be made to minimize dropouts and missing assessment data. Subjects should be reminded of the importance of providing assessments as per protocol, and study personnel should be vigilant in ensuring assessments are completed as scheduled.

Nonetheless, as subjects may elect to be withdrawn from study treatments or evaluations without prejudice, it is inevitable that there will be missing data. Subjects who elect to discontinue their randomized treatment but consent to continue in the study may provide on-study but off-treatment assessments which will aid in providing sensitivity analyses for the co-primary endpoints.

The handling of missing data in the statistical analyses of the efficacy endpoints will be fully detailed in the SAP.

No imputation of values for safety endpoints will be made. The SAP will provide methods for handling partial or completely missing assessment dates or missing adverse event severity.

9.4.3 SAFETY ANALYSES

9.4.3.1 ADVERSE EVENTS AND SERIOUS ADVERSE EVENTS

A TEAE is defined as:

- A new event that occurs during or after first dose of study treatment or,
- Any event present at baseline that worsens in either intensity or frequency after first dose of study treatment.

TEAEs and SAEs will be summarized.

Adverse events will be coded using the Medical Dictionary for Regulatory Activities (MedDRA). The incidence and percentage will be tabulated by preferred term (PT) and system organ class (SOC). An event that occurred 1 or more times on treatment period will contribute 1 observation to the numerator and denominator comprise all safety subjects exposed to etokimab. If the intensity or seriousness of the TEAE changes, the overall intensity or seriousness will be the maximum intensity or seriousness of the multiple occurrences. The TEAEs, SAEs, TEAEs leading to treatment discontinuation, and TEAEs leading to withdrawal of subject will be tabulated for each treatment group. Summaries will also be presented by relatedness to the study drug and the severity of the TEAE.

Listings of AEs, TEAEs, TEAEs leading to death, SAEs, and TEAEs that led to discontinuation from the study or of the study drug will be presented.

Injection site reaction will be reported separately by treatment.

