3 OBJECTIVES AND ENDPOINTS

OBJECTIVES	ENDPOINTS	JUSTIFICATION FOR ENDPOINTS
Primary		EIVEI OIIVIS
To evaluate the efficacy of etokimab compared to placebo in the treatment of subjects with CRSwNP following a 16-week treatment period	 Change from baseline to Week 16 in bilateral endoscopic NPS Change from baseline to Week 16 in Sino-Nasal Outcome Test (SNOT-22) scores 	Change in NPS and SNOT-22 are outcome measures that have been established as clinically relevant for assessing treatment response to mAbs for the management of CRSwNP symptoms
Secondary		
To evaluate the effectiveness of etokimab compared to placebo in subjects with CRSwNP in relieving clinical symptoms	 Time to first response (≥ 1 point improvement) in NPS Responder analysis: response defined as a reduction of at least 1 point from baseline to Week 16 in NPS Responder analysis: response defined as a reduction of at least 12 points from baseline to Week 16 in SNOT-22 Change from baseline to Week 16 in sense of smell as assessed by the University of Pennsylvania Smell Identification Test (UPSIT) 	These endpoints are outcome measures that have been established as clinically relevant for assessing treatment response of mAbs for the management of CRSwNP symptoms
To assess the safety and tolerability of etokimab in subjects with CRSwNP compared to placebo following a 16-week treatment period	 Incidence of AEs and TEAEs Incidence of SAEs Changes in clinical laboratory tests (hematology, chemistry, and urinalysis) Changes in vital signs (BP, temperature, respiration rate, and pulse rate) Changes in ECG parameters Immunogenicity (ADA and neutralizing ADA) 	These endpoints are outcome measures that have been established as clinically relevant for assessing the safety and tolerability of mAbs for the management of CRSwNP symptoms
To assess the pharmacokinetics (PK) of etokimab in human serum in subjects with CRSwNP following subcutaneous (SC) administration	 CL/F Apparent volume of distribution C_{max} Time of maximum concentration (t_{max}) 	These PK endpoints are PK-specific outcome measures that have been established as clinically relevant for assessing the PK of mAbs for the

OBJECTIVES	ENDPOINTS	JUSTIFICATION FOR ENDPOINTS
	 Area under the concentration-time curve from time 0 to the time of the last quantifiable concentration (AUC_{tau}) Apparent terminal half-life (t_{1/2}) will also be determined for etokimab after SC administrations, as possible 	management of CRSwNP symptoms
Exploratory		

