8.6.2 DEFINITION OF SERIOUS ADVERSE EVENTS

A SAE includes any event that results in any of the following outcomes:

- Death
- Life-threatening (ie, the subject was, in the opinion of the Investigator, at immediate risk of death from the event as it occurred. It does not apply to an AE that hypothetically might have caused death if it were more severe.)
- Persistent or significant disability/incapacity or substantial disruption of the subject's ability to carry out normal life functions
- Requires in-patient hospitalization or prolongs hospitalization (ie, a prolonged hospitalization beyond the expected length of stay; hospitalizations for elective medical/surgical procedures, scheduled treatments, or routine check-ups are not SAEs by this criterion)
- Congenital anomaly/birth defect (ie, an adverse outcome in a child or fetus of a subject exposed to the molecule or IP before conception or during pregnancy)
- Does not meet any of the above serious criteria but based upon appropriate medical judgment may
 jeopardize the subject or may require medical or surgical intervention to prevent one of the
 outcomes listed above (ie, is a significant or important medical event)

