9.3 ANALYSIS SETS

The analysis sets for evaluating the efficacy, safety, and pharmacokinetics of etokimab are defined in Table 2.

Table 2. Analysis Sets

Analysis Set	Description
Safety Analysis Set	The safety analysis set will include all randomized subjects who receive 1 dose of etokimab or placebo. The safety analysis set will be used for all safety analyses. Subjects will be analyzed as treated.
Full Analysis Set	The full analysis set (FAS) will include all randomized subjects who receive 1 dose of etokimab or placebo and have baseline and at least 1 post baseline NPS and/or SNOT-22 scores up to Week 16. The full analysis set will be used for all efficacy analyses. Subjects will be analyzed as randomized.
PP Analysis Set	The PP (Per Protocol) analysis set will include all subjects in the FAS analysis set who do not have major protocol violations that would affect the evaluation of the primary efficacy endpoints.
PK Analysis Set	The PK analysis set will include all subjects in the safety analysis set who have at least one quantifiable postdose PK sample available and who do not have events or protocol deviations or events with the potential to affect PK concentrations. The PK analysis set will be used for all PK analyses.

Abbreviations: FAS = Full analysis set, PP = Per protocol, PK = Pharmacokinetics.

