9.4.4.2 SUBJECT CHARACTERISTICS AND MEDICAL HISTORY

Subject characteristics obtained at Screening will be summarized for all subjects taking etokimab. Subject characteristics may include, but are not limited to age, gender, height, weight, and BMI.

Summaries will include descriptive statistics for continuous variables (sample size [n], mean, SD, median, minimum, and maximum) and for categorical variables (sample size, frequency, and percent).

Medical history will be coded using the MedDRA dictionary latest version and listed for all subjects.

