6. GENERAL ASPECTS FOR STATISTICAL ANALYSIS

6.1. General Methods

The following conventions will be utilized in the analyses:

- The final statistical analysis will not be performed until all the reportable data have been collected, queries answered, and the database locked.
- All relevant individual subject data will be provided in data listings sorted by treatment arm and subject number. The following treatment group labels will be used: "Placebo", "etokimab Q8W", and "etokimab Q4W". Where subjects who were not randomized are included in listings, the treatment arm will be indicated as "Not Assigned" or "Not Randomized".
- Tabulations will be produced for appropriate demographic, baseline, efficacy and safety parameters. All tabular summaries will be presented by treatment arm as indicated above. A total column may be included under "All Subjects" where necessary or appropriate.
- In general, continuous variables will be summarized by descriptive statistics including the number of observations (n), mean, standard deviation (SD) or standard error (SE), median, minimum (min), and maximum (max); the lower (Q₁) and upper quartile (Q₃) may be included in some summaries if deemed necessary or important. The same number of decimal places as the raw data will be presented when reporting min and max, 1 more decimal place than in the raw data will be presented when reporting mean, median, lower and upper quartiles and 2 more decimal places than in the raw data will be presented when reporting SD or SE.
- Categorical data will be summarized using the number of observations (n), frequency, and percentage of subjects in the relevant analysis set and treatment group falling within each category.
- Unless otherwise specified, where there are multiple measurements at a post-baseline visit or time of assessment, the value closest to the target date within the specified window for the assessment visit will be used for analysis.
- For numerical variables, change from baseline will be calculated as the value of interest at the time of measurement minus the corresponding baseline value.
- All statistical tests will be two-sided; unless otherwise indicated; two-sided p-values < 0.05 will be regarded as statistically significant, and confidence intervals (CI) will be 2-sided and have 95% confidence level.
- All subject data will be included in listings.
- Data analyses will be conducted using validated computer software (e.g. SAS[®] Version 9.4 or higher).

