10.2. Adverse Events

For the purpose of this study, an adverse event (AE) is any untoward medical occurrence (e.g., sign, symptom, disease, syndrome, intercurrent illness, clinically significant abnormal laboratory finding, injury, or accident) that emerges or worsens following initial administration of the study medication (eg., mometasone furoate nasal spray) and until the end of study participation. The untoward medical occurrence may not necessarily have a causal relationship to the administration of the investigational product. An AE can therefore be any unfavorable and/or unintended sign (including a clinically significant abnormal laboratory result), symptom, or disease temporally associated with the use of a medicinal (investigational) product, whether or not related to the medicinal (investigational) product.

A serious adverse event (SAE) is any untoward medical occurrence that at any dose: results in death, is life-threatening, requires hospitalization or causes prolongation of existing hospitalization.

A treatment-emergent AE (TEAE) is an AE that occurs or worsens in severity after any exposure to the investigational product (etokimab or placebo). If an AE starts between the screening visit and the randomization visit, and is ongoing at the time of treatment initiation, it may be deemed treatment emergent if it worsens in severity/severity. In that case, a separate event is to be recorded in the subject's eCRF indicating the worsened severity.

Section 6.3.4 of this SAP provides conventions for handling missing dates for AEs, for determining treatment emergence in the presence of missing data, and for assigning severity and treatment-relatedness in the presence of partial or missing start/stop AE dates.

All adverse events will be coded using MedDRA version 21.0 or higher. The TEAE reporting period begins with administration of the first dose of study medication on Day 1 and continues until the Visit 7 (Week 16 visit, or 28 days after the last dose of study medication). The Safety Follow-Up AE reporting period begins 29 after the last dose of study medication through completion of the Safety Follow-Up Period (Week 24 visit).

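### Two safety rules are wrong as written: SAP 10.2 keeps three of the protocol's six SAE criteria, and Protocol 9.4.3.1 gives placebo no adverse-event denominator

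*Protocol*

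**What the plan says.** **Seriousness.** SAP 10.2 calls an event serious if, at any dose, it "results in death, is life-threatening, requires hospitalization or causes prolongation of existing hospitalization". The sentence reads as a complete definition: it is not offered as an example and does not refer to the protocol. Protocol 8.6.2 lists six criteria, among them "Persistent or significant disability/incapacity or substantial disruption of the subject's ability to carry out normal life functions". Its hospitalization criterion excludes elective procedures, scheduled treatments and routine check-ups. Protocol Appendix B adds that a spontaneous abortion is in every case an SAE. SAP 10.2.1 then plans tables of serious TEAEs and of serious treatment-related TEAEs, and a separate listing of SAEs.

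**Denominator.** Protocol 9.4.3.1 says that an event occurring once or more will "contribute 1 observation to the numerator and denominator comprise all safety subjects exposed to etokimab". The same paragraph says that TEAEs, SAEs and "TEAEs leading to withdrawal of subject will be tabulated for each treatment group". Protocol Table 2 states: "The safety analysis set will include all randomized subjects who receive 1 dose of etokimab or placebo", and assigns that set to all safety analyses. SAP 6.1 bases categorical summaries on the "percentage of subjects in the relevant analysis set and treatment group falling within each category", and Protocol 9.4.1 has an equivalent rule.

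**Baseline.** Protocol 9.4.4.2 follows the same pattern as the denominator clause: "Subject characteristics obtained at Screening will be summarized for all subjects taking etokimab". SAP 7.4 summarizes demographics for the FAS and the Safety Analysis Set, both of which include placebo.

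**Declared changes.** SAP Section 12 records only the change to the nocturnal-awakenings analysis.

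**The concern.** The incidence of AEs and TEAEs and the incidence of SAEs are listed secondary endpoints, under the objective "To assess the safety and tolerability of etokimab in subjects with CRSwNP compared to placebo following a 16-week treatment period". An incidence needs one rule for what is counted and one for what it is divided by, and the two documents should agree on both.

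They do not. The SAP's rule for what counts as serious is narrower than the protocol's in three respects and, with the elective-admission exclusion gone, wider in one. The protocol's rule for the denominator has no place for the comparator arm. Someone who took either sentence at face value would produce a table that does not estimate the stated endpoint. For seriousness, nothing else in the SAP corrects the wording or says where the classification comes from.

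**Working it through.** **Step 1. Count the seriousness criteria.**

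| Criterion | Protocol 8.6.2 | SAP 10.2 |
|---|---|---|
| Death | yes | yes |
| Life-threatening | yes | yes |
| Hospitalization or its prolongation | yes, elective admissions excluded | yes, no exclusion |
| Disability or incapacity | yes | no |
| Congenital anomaly or birth defect | yes | no |
| Important medical event | yes | no |

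The protocol has 6 and the SAP 3, so 6 − 3 = 3 are missing, along with one exclusion.

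**Step 2. Classify the same events under each possible source.** The SAP could mean either the investigator's reported seriousness (Protocol 8.6.2) or its own sentence.

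| Event | Investigator, under the protocol | SAP wording, literally |
|---|---|---|
| Spontaneous abortion, no admission, not life-threatening | SAE (Appendix B) | not an SAE |
| Important medical event, no admission, not life-threatening | SAE | not an SAE |
| Disability, no admission, not life-threatening | SAE | not an SAE |
| Elective admission only | not an SAE by the hospitalization criterion | could be counted |

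The wording can therefore move the SAE count in either direction. If the tables use the reported seriousness, none of these rows matters.

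**Step 3. Look for the source in the SAP.** SAP 10.2.1 tabulates serious TEAEs without saying how seriousness is determined. SAP 6.3.4.2 fills in missing severity and missing relationship but has no rule for seriousness. No SAP section reclassifies reported events, and none says that the reported assessment is the one used.

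**Step 4. Size the denominators.** Protocol 9.2 takes 27 subjects per arm and allows for 18% dropouts and missing data: 27 / (1 − 0.18) = 32.9, which reproduces the planned 33. With three arms:

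- subjects exposed to etokimab: 2 × 33 = 66;
- placebo subjects: 33;
- whole Safety Analysis Set, if every randomized subject is dosed: 3 × 33 = 99.

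The clause in Protocol 9.4.3.1 covers the 66 and none of the 33 on placebo. A placebo percentage is undefined under it. By-group percentages over the Safety Analysis Set use about 33 in each arm.

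**Step 5. Check which text prevails.** The clause is contradicted by its own paragraph (tabulation by treatment group), by Table 2 (the safety set includes placebo), by Protocol 9.4.1 (percentages by analysis set and treatment group) and by SAP 5.2, 6.1, 10 and 10.2.1. Protocol 9.4.1 also leaves full analysis details to the SAP. Tables produced under the SAP should therefore have the correct denominator.

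**The case against.** The strongest reply is that both sentences are drafting slips with no operational effect. The denominator clause is one ungrammatical fragment, overridden within its own paragraph and by every other relevant section. On seriousness, sites work from the protocol: Protocol 8.6.6 has the investigator report any SAE within 24 hours, and 8.6.2 tells the investigator what one is. SAP 10.2 merely describes. For an event to be lost or added, a programmer would have to override reported seriousness without being told to.

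Most of this stands. It limits the consequence but does not make either sentence correct. It is also weaker for seriousness than for the denominator: the SAP contains the right denominator elsewhere, but it nowhere contains the right SAE definition or names the source.

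Three stronger readings are tempting and are not supported.

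- A reader might infer that the placebo rate, or every arm's rate, would be halved by dividing by 66 instead of 33. The protocol does not say to divide placebo events by etokimab-exposed subjects, and pooling the two etokimab arms would conflict with tabulation by group.
- A reader might infer that SAEs will be missed, or elective admissions counted. That follows only if the tables are built from the SAP sentence, which no document instructs.
- A reader might cite the Phase 1 SAE of decreased neutrophils as an event the SAP would lose. Protocol 2.3.1 does not say which criterion made it serious.

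**Conclusion.** Two stated rules are wrong as written.

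1. **SAE definition (SAP 10.2).** It omits three of six protocol criteria and the elective-admission exclusion, conflicts with Appendix B on spontaneous abortion, and is not declared as a change. Read literally, the serious-TEAE tables and the SAE listing would not match the protocol's endpoint. The effect on counts is zero if the investigator's assessment is used. If the SAP wording is used, the effect cannot be quantified from the documents, because they give no expected SAE numbers by criterion.
2. **AE denominator (Protocol 9.4.3.1).** It leaves the placebo arm, about 33 of 99 planned subjects, without a denominator. This is an internal contradiction in the protocol that tables following the SAP should not carry forward.

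Protocol 9.4.4.2 is a minor companion to the second point and does not bear on AE incidence.

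The arm sizes are planned numbers and assume that all randomized subjects are dosed. The conclusion about consequences assumes that the SAP governs the tables. The correction should be made, but the documents do not show that any planned safety result would change.

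**What to change.** - **SAP 10.2:** replace the SAE sentence with the full definition in Protocol 8.6.2, including the elective-admission exclusion, or cite that section. Add that SAE tables and listings use the investigator's seriousness assessment made under it.
- **Protocol 9.4.3.1:** state that the denominator for each percentage is the number of Safety Analysis Set subjects in that treatment group.
- **Protocol 9.4.4.2:** extend the summary of subject characteristics to all arms, by treatment group, in line with SAP 7.4.

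The cost is a few sentences across the two documents. No new data, analysis or change to site procedures is needed. If the protocol is not to be amended again, a line in SAP Section 12 could record that by-group denominators and all-arm baseline summaries replace the two protocol sentences.

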9.4.3.2 DEATHS

Subject deaths will be presented in a by-subject listing.

9.4.3.3 PHYSICAL EXAMINATIONS, 12-LEAD ECG, VITAL SIGNS, AND CLINICAL SAFETY LABORATORY TESTS (HEMATOLOGY, BIOCHEMISTRY, AND URINALYSIS)

Summaries and listings of data for both limited and complete physical examination findings, vital signs, hematology, biochemistry, and urinalysis laboratory tests will be presented. Appropriate descriptive statistics will be summarized for the observed value at each scheduled assessment and for the corresponding change from baseline.

For hematology and biochemistry tests, listings of subject data will also flag any abnormal or out-of-range values. Clinically significant changes in the laboratory test parameters will be summarized and listed. Hematology and clinical laboratory data will be reported in System International units.

Descriptive statistics will be used to present the safety outcomes including, physical examination results, weight, BMI, 12-lead ECG, vital signs measurements, and clinical laboratory test results.

Change from baseline will also be summarized for vital signs measurements, and clinical laboratory test results.

All ECG data results (normal/abnormal) will be summarized using frequency and percentages. Clinically significant abnormalities will be presented in by subject listings.

9.4.4 BASELINE DESCRIPTIVE STATISTICS

9.4.4.1 SUBJECT DISPOSITION

A tabular presentation of the subject disposition will be provided. It will include the number of subjects screened, randomized, treated, completed as well as the number of study discontinuations, with reasons for discontinuation, and major protocol deviations or violations.

A listing will be presented to describe date of Screening, assigned treatment, screen failed with reason, completion or early withdrawal, and the reason for early discontinuation, if applicable, for each subject. A list of protocol deviations/violations will be identified and discussed with the Investigator and Sponsor in dry run to categorize as major or minor and the same will be reported.

9.4.4.2 SUBJECT CHARACTERISTICS AND MEDICAL HISTORY

Subject characteristics obtained at Screening will be summarized for all subjects taking etokimab. Subject characteristics may include, but are not limited to age, gender, height, weight, and BMI.

Summaries will include descriptive statistics for continuous variables (sample size [n], mean, SD, median, minimum, and maximum) and for categorical variables (sample size, frequency, and percent).

Medical history will be coded using the MedDRA dictionary latest version and listed for all subjects.

